# **Awake Prone Positioning to Reduce Invasive VEntilation in COVID-19 Induced Acute Respiratory failure (APPROVE-CARE)**

### *Study Summary*

The coronavirus disease 2019 (COVID-19) outbreak is a pandemic associated with a pneumonia which can worsen rapidly into respiratory failure known as acute respiratory distress syndrome (ARDS). There is a high rate of mortality in patients with severe respiratory failure requiring mechanical ventilation. Adjunctive therapies constitute an important part of the management of early moderate to severe ARDS. In patients with confirmed moderate-severe ARDs receiving invasive mechanical ventilation, prone position promotes lung homogeneity, improves gas exchange and respiratory mechanics permitting reduction of ventilation intensity, and reducing lung injury. Prone positioning has been demonstrated to save lives and is recommended in evidence-based guidelines for the management of moderate-severe ARDS.

The use of proning outside of mechanically ventilated patients to improve gas exchange and reduce the end for invasive ventilation has not been extensively studied outside of case series. Maintaining self ventilation is associated with increased aeration of dependent lung regions, less need for sedation, improved cardiac filling, and better matching of pulmonary ventilation and perfusion and thus oxygenation.

In this protocol, we outline details for a randomized clinical trial to determine whether placing patients who have hypoxemia related to COVID19 into a prone position can improve oxygenation and reduce the requirement for mechanical ventilation. If effective, this simple intervention could be widely and rapidly implemented, potentially reducing the need for ICU admission and invasive ventilation, and potentially even saving lives.

**2. Study sponsor**

Clinical Research Facility, National University of Ireland, Galway

### **3. Background and rationale**

#### **a. COVID-19 and Hypoxemia**

Severe Acute Respiratory Syndrome Corona Virus 2 (SARS-CoV-2) first appeared in Wuhan China in December 2019. It has since spread and was declared a worldwide pandemic by the World Health Organisation in March 2020.(1) Its main route of infection are respiratory droplets and contact transmission. Many infections will be asymptomatic or mild, but a subset require hospitalization and admission to critical care is associated with a high morbidity and mortality from the disease. Acute respiratory distress syndrome requiring mechanical ventilation is associated with a 40-60% mortality. To date, there are no specific pharmacological therapies currently although many are being trialled.(2)

#### **b. Prone position physiology**

Prone position is a non-pharmacological treatment used in patients with severe ARDS which has proven mortality benefits in this population. (3) Physiological studies have shown differences in ventilation pressures in distinct regions of the chest depending on whether one is in the prone or supine position. While breathing in a supine position, the ventral chest wall is lifted by a driving pressure driven by the difference between pleural pressure and atmospheric pressure ( $P_{\text{pleural}} - P_{\text{atmospheric}}$ ): the diaphragm moves caudally ( $P_{\text{pl}} - P_{\text{abdomen}}$ ), and the dorsal chest wall moves minimally as lying in contact with a rigid surface. In the supine position, there is a reduction in alveolar size from sternum to vertebra in the supine position at the end of the expiration. This phenomenon has also been clearly identified with CT scans (6-9), and leads to a greater expansion of the nondependent regions and lesser expansion of the dependent parenchyma (6-8).

Contrarily while prone, the dorsal chest wall lifts, the diaphragm shifts similarly to supine position, and the ventral chest wall, now in contact with the firm surface of the bed, is impeded from expanding (8). In the prone position the gravitational forces compress the ventral region, but this effect is damped by regional expansion due to shape matching between lung parenchyma and vertebrae. As the lung mass is anatomically greater in dorsal regions (nondependent when prone) than in ventral region (dependent when prone), the increased aeration and recruitment of the dorsal region tends to exceed the decreased aeration and derecruitment of the ventral regions. That generates a more homogenous ventilation across the entire lung(6). Furthermore, when an individual is supine the heart compresses the medial posterior lung parenchyma (10) and the diaphragm compresses the posterior-caudal lung parenchyma, with the abdominal contents displacing the diaphragm cranially (8,10). Compression by either the heart and/or the diaphragm may exaggerate dependent lung collapse in the supine position (9). During prone ventilation, the heart becomes dependent, lying on the sternum, potentially decreasing medial-posterior lung compression (10). In addition, the diaphragm is displaced caudally, decreasing compression of the posterior-caudal lung parenchyma. A further advantage observed in prone position is both an improvement of ventilation/perfusion match and an increase in cardiac output: the latter is thought to be due to the effect of increased lung recruitment and reduction in hypoxic pulmonary vasoconstriction, resulting in increases in right ventricular preload and decreased right ventricular afterload and a decrease in pulmonary vascular resistance (11,12). An important recent study by Guerin et al. showed that prone positioning applied for at least 16 hours per day in patients with ARDS and  $\text{PaO}_2/\text{FiO}_2 < 150$  mmHg significantly reduced 28-day mortality (16% vs 32%).(15) From currently available evidence, prone positioning may be of value even if there is no improvement in gas exchange [10-14].

**c. *Experience with awake prone positioning in self-ventilating patients***

Prone position results in improved ventilation and blood flow ratios. In mechanically ventilated and often paralysed patients, proning requires a high nursing input and patients are at risk for pressure sores related to the position. These issues are less pertinent in patients who are self-ventilating. Proning self-ventilating patients is not commonly carried out as patients with reduced oxygenation generally require assisted ventilation. However, avoidance of mechanical ventilation by improving oxygenation may be importance in COVID19 as outcomes for patients who require mechanical ventilation are poor and resources become limited. We have noted improvement with proning in self ventilating patients at both ward level and in the ICU for patients with confirmed COVID19 and in a patient without COVID19 with ARDS.

**d. *Rationale for treating patients with COVID19 pneumonia with awake prone positioning***

Patients with COVID19 that require invasive mechanical ventilation have a high mortality. We hypothesis that early proning for self-ventilating patients with suspected or confirmed COVID19 who have hypoxemia (spO2 <94%) despite high flow nasal cannula (fiO2 40%) will result in improved oxygenation, reduced work of breathing and a reduced the need for invasive mechanical ventilation.

#### **4. Study Aims and Objective**

##### **a. Research hypothesis**

In patients that are hypoxic secondary to COVID19, the use of prone positioning will result in a reduction in requirement for invasive mechanical ventilation. Key secondary hypothesis include that prone positioning will result reduced requirement for assisted ventilation, in improved oxygenation as measured by either S/F or P/F ratio, reduced work of breathing.

##### **b. Study aim**

The study aims to assess the effect of prone positioning in patients who have hypoxemia related to COVID19 on:

- need for mechanical ventilation
- Improvement in oxygenation as measured by S/F or P/F ratio
- Patient work of breathing as measured by the respiratory distress observation scale
- tolerability of the position as measured by the total number of hours in prone position

##### **c. Study objectives**

###### **Primary objective**

To assess the effect of awake prone positioning on requirement for mechanical ventilation or death in patients with suspected or confirmed COVID 19 infection.

###### **Secondary objective**

To assess the effect of prone positioning on:

- Length of time tolerating prone positions measured in minutes from prone to request to return to supine position or emergency repositioning if required
- SpO2: FiO2 ratio (as a surrogate marker of P/F ratio) measured before proning and 1 hours after proning or P/F ratio where arterial line available
- Number requiring increase in ventilatory assistance (CPAP+BIPAP+IMV etc)
- Work of breathing assessment

#### **5. Study Details**

##### **a. Study design**

Multi centre open label randomized controlled study in which patients are randomized to awake prone positioning or standard care. This trial is registered with ClinicalTrials.gov (NCT04347941). This trial is part of a prospective meta-trial listed in appendix 1.

##### **b. Study timeline**

Study will begin 5th June 2020 and until 28 days following the last enrolled patient

##### **c. End of study**

Study will continue until 28 days after the last enrolled patient or for 6 months until October 2020, depending on levels of enrolment.

## 6. **Study outcome measure**

### a. **Primary outcome measure**

Requirement for invasive mechanical ventilation or death by 28 days post enrolment

### b. **Secondary outcome measure**

- Length of time tolerating prone positions measured in minutes from prone to request to return to supine position or emergency repositioning if required
- SpO2 : FiO2 ratio (as a surrogate marker of P/F ratio) measured before proning and 1 hours after proning or P/F ratio where arterial line available
- Number requiring increase in ventilatory assistance (CPAP+BIPAP+IMV etc)

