#### ***d. Allocation and Randomisation***

Within 6 hr of fulfilling inclusion criteria, a patient will be randomly allocated either to the prone positioning group or the control group (HFNC alone with no prone positioning therapy). Patients will be randomly allocated to either arm of the study at a ratio based on a 1:1 basis using a REDCAP randomisation process. Randomization will be stratified by site using tables of random permutations using the RECAP database for randomization. The random block length is 4, and random numbers are generated by computer.

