### ***11. Statistical Considerations***

#### ***a. Sample size***

From ICNARC data on patients admitted to ICU with COVID19, 60% required advanced respiratory support. From this, we propose a 60% intubation rate in this cohort as defined above and that proning will decrease it to 40%. From this, 97 patients per group for a beta of 0.2 and alpha 0.05, requiring the need to recruit 196 patients. Interim analysis of data will be conducted using aggregated data as part of the Awake Prone Positioning in COVID Meta-Trial.

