#### ***b. Analysis population***

Data will be analysed on an intention to treat basis with all data for patients who consented to be involved included in baseline data analysis. Outcome data will be analysed for all patients who were positioned in the prone position for any length of time. A further per protocol analysis will be carried out on all patients who tolerated at least 1 hour of the daytime proning time and at least 2 hours of the night time proning period in any 24 hour period. Patients who were rescue prone will be considered a protocol deviation and will be studied as a group. Definition of the two groups: The

patients who receive the prone positioning are classified as prone positioning group. The patients who receive HFNC alone are classified as HFNC group. Comparisons between the two groups: Quantitative continuous variables are given as either means ( $\pm$ SDs) or medians (with inter-quartile ranges) are compared using the unpaired Student's t test or the Mann-Whitney test. Qualitative or categorical variables are compared with the chi square test or the Fisher's exact test. ANOVA for paired tests to compare the same variables collected at different time points are used. The cumulative probability of remaining on spontaneous breathing are compared with the Kaplan-Meier estimate of survival and the log-rank test to compare the two groups. Univariate and multivariate analyses of risk factors for PP failure are performed with logistic regression. All analyses are in intention to treat, and the level of significance is set at 0.05.

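### The oxygenation outcome is timed only by proning, so the available text defines no control-arm value for a key secondary hypothesis

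*Combined protocol and SAP*

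**What the plan says.** Section 4a lists, among the key secondary hypotheses, that proning will result "in improved oxygenation as measured by either S/F or P/F ratio". Section 4b repeats this as an aim: "Improvement in oxygenation as measured by S/F or P/F ratio".

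The measure is defined twice, in the same words, under the secondary objective in Section 4c and the secondary outcomes in Section 6b. It is the SpO2:FiO2 ratio (S/F), "measured before proning and 1 hours after proning or P/F ratio where arterial line available". Section 9d randomises 1:1 against a "control group (HFNC alone with no prone positioning therapy").

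For continuous variables, Section 11b offers an unpaired t test or Mann-Whitney test between the two groups. It adds "ANOVA for paired tests to compare the same variables collected at different time points are used" and closes with "All analyses are in intention to treat". None of these statements names S/F, P/F or a time point. The same section also says "Outcome data will be analysed for all patients who were positioned in the prone position for any length of time".

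Section 10 is headed as a schedule of assessment but gives no assessment times. It points to the case report form in Appendix B, which is not in the text available for this review.

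**The concern.** A hypothesis about the effect of proning in a randomised trial needs a value of the outcome in each arm, taken at comparable times. Here both readings are fixed by an event that happens only in the prone arm. An analyst who follows the definition has a pair of readings in proned patients and nothing specified to set against it.

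At stake is how a positive oxygenation result could be read. Patients enter because their saturation is low, and they receive other care at the same time. Some would probably improve over the following hours without proning. A before/after change cannot separate that improvement from an effect of position. Randomised controls could, but the definition does not use them.

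**Working it through.** **1. The definition set against the design.**

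- First reading, before proning (4c, 6b): defined in the prone arm, not in controls.
- Second reading, one hour after proning (4c, 6b): defined in the prone arm, apart from the choice of session; not defined in controls.
- Primary outcome (6a): counted to 28 days from enrolment, an anchor that exists in both arms.
- Randomisation (9d), within 6 hours of meeting the inclusion criteria: also common to both arms, but not used for S/F.

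No other section available gives a time for an S/F or P/F reading in controls.

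**2. How many patients this covers.** Section 11a gives "97 patients per group for a beta of 0.2 and alpha 0.05, requiring the need to recruit 196 patients", for 60% versus 40%. To reproduce this with two-sided alpha 0.05, power 0.80 and pooled variance:

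n = [1.960 × √(2 × 0.5 × 0.5) + 0.842 × √(0.6 × 0.4 + 0.4 × 0.6)]² / 0.2² = (1.386 + 0.583)² / 0.04 ≈ 96.9, so 97 per group.

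The plan's figure is confirmed. Then 2 × 97 = 194, and 196 recruited at 1:1 is 98 per arm. Patients allocated to an arm with no defined oxygenation value: 97/194 = 98/196 = 50%. Controls proned as rescue (11b) could have readings, but only as a selected subgroup.

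**3. What the literal definition yields.** It yields a paired change in proned patients. Section 7c requires SpO2 below 94% on FiO2 40%, so S/F at qualification is below 94/0.40 = 235. Selection on a low value makes some later rise plausible without any effect of position. The documents give neither its size nor an SD for S/F.

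The following is an illustration only. Assume 97 proned patients, a two-sided 0.05 paired test (normal approximation), no proning effect, and a background change of d SDs of the change score. The chance of a significant result is 1 − Φ(1.960 − d√97) + Φ(−1.960 − d√97):

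- d = 0: 0.05
- d = 0.1: 0.17
- d = 0.2: 0.50
- d = 0.3: 0.84
- d = 0.5: 1.00 (0.998)

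The values of d are assumptions and do not come from the plan.

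**4. What a two-arm comparison could detect.** With one reading per patient in both arms, the difference detectable with 80% power is (1.960 + 0.842) × √(2/97) = 0.40 SD. The result with 98 per arm is also 0.40. This takes no account of baseline adjustment or of patients without a reading.

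**The case against.** The strongest reply is that a comparison of arms is probably intended. Section 11b compares two groups, lists unpaired tests for continuous variables and claims intention to treat throughout. Reading times would normally sit in the case report form, and Appendix B was not available. This stands as a limit on the finding. A reader might infer that the trial collects no oxygenation data in controls, or that a one-arm analysis is settled. The documents support neither. What remains is that the unpaired tests have no defined control value to act on. Even if the form holds readings in both arms, the outcome definition does not say which to compare.

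A second reply is that a before/one-hour reading is a recognisable measure of immediate response to turning, and that another listed outcome, time tolerated prone, can exist only in proned patients. That is fair, and it is a reason to keep the measure as description. It does not meet Section 4a, which states a hypothesis about improved oxygenation.

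Third, the related gaps in the definition are smaller. Section 9 implies more than one session a day and asks for at least 30 minutes if tolerated, so a session could end before a reading taken one hour from its start. However, patients are also asked to stay prone as long as they can, the hour might run from the end of the session, and the frequency of short sessions is unknown. Nothing says that S/F and P/F will be pooled; the text only leaves the rule unstated.

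**Conclusion.** The point holds in limited form. The available text defines the oxygenation outcome only for proned patients, so as written it cannot test the Section 4a hypothesis between randomised groups. It leaves 50% of the planned patients without a defined value. That figure follows from 1:1 allocation and does not measure bias, whose size cannot be derived from the documents. The conclusion rests on the text available and would ease if Appendix B sets common reading times and the outcome definition is tied to them.

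A reader might infer that the primary outcome or the sample size is compromised. The S/F timing does neither: the primary outcome runs from enrolment in both arms, and 97 per group reproduces. The Section 11b sentence limiting outcome data to proned patients is a different matter. It covers every outcome, including the primary, and conflicts with that section's own intention-to-treat statement, so it should be handled as a separate finding. The correction here should be made, but it concerns one secondary outcome.

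**What to change.** - In Sections 4c and 6b, define S/F in both arms at randomisation and at the same pre-stated time or times after it, using existing case report form readings if there are any.
- In Section 11, compare the randomised groups by intention to treat, adjusted for baseline S/F. State in advance how patients intubated or dead before the time point are counted; otherwise the last-observation rule in Section 11c could apply to them by default.
- Use S/F for the main comparison and report P/F separately in patients with an arterial line.
- Keep the before/one-hour change as a description of the prone arm. Say which session it refers to and whether the hour runs from its start or its end.
- State as a limitation that FiO2 is titrated by unblinded staff. A common time point deals with time trend and regression to the mean, but not with titration that differs by arm.

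The cost is routine bedside readings at set times in controls, a small form edit if Appendix B does not already capture them, and a few lines of text. The sample size does not change.

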## 7. **Patient Eligibility**

### a. **Study setting**

A monitored ward or ICU in which patients with confirmed or suspected COVID19 are receiving high flow nasal cannula

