## **9. Assignment of intervention**

Awake prone positioning will be performed before or 1 hour after meal. Call bell will be given to the patient and an oxygen probe will be attached to the patient to monitor spO2 during the procedure. Before PP, all the I.V. lines and nasal cannula will be checked by clinicians. Awake prone positioning will be performed by patient under the supervision of clinicians. Assistance will be offered if needed. If tolerated, PP will be maintained for at least 30 minutes, until the patients feel tired to keep that position. Patients will be informed to maintain prone position as long as they can. FIO2 will be adjusted to maintain SpO2 at 92-95%. Protocol for sedation and comfort evaluation during PP: No sedation will be used during the PP on ward. The patients are monitored by bedside respiratory therapist and nurses for their comfort and tolerance for the PP at 5mins, 30 minutes after PP for the first PP in each day.

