### **b. Weaning criteria**

- Patients' PaO2/FIO2 > 300, or SpO2/FIO2 > 340

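### The secondary oxygenation outcome allows S/F in some patients and P/F in others, with no rule for keeping the two scales apart

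*Combined protocol and SAP*

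**What the plan says.** Section 6b defines oxygenation by S/F, described as a surrogate for P/F, "measured before proning and 1 hours after proning or P/F ratio where arterial line available". The secondary objective in section 4c uses the same wording. The hypothesis in section 4a expects "improved oxygenation as measured by either S/F or P/F ratio", and the aim in section 4b reads "Improvement in oxygenation as measured by S/F or P/F ratio".

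Four other parts of the protocol bear on this:

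- Section 9b (weaning) gives the two ratios different cut-offs: "Patients' PaO2/FIO2 > 300, or SpO2/FIO2 > 340".
- Section 7a allows more than one care setting: "A monitored ward or ICU". Randomisation (section 9d) is stratified by site only, and the trial is open label.
- Section 9 states that "FIO2 will be adjusted to maintain SpO2 at 92-95" per cent.
- Section 11b offers an unpaired t test or Mann-Whitney test for continuous variables, and a paired ANOVA for the same variable at different times. It does not mention the two ratios.

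**The concern.** Read as written, the rule puts a patient with an arterial line on one scale and a patient without on another, under one outcome name. What decides the scale is a feature of care that can change after open-label allocation. Nothing stops a patient being read on one scale before proning and on the other an hour later.

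If values are then compared between arms as they stand, two things follow. The offset between scales adds variation that has nothing to do with treatment. Any difference between arms in the share of patients with lines also appears as a difference in oxygenation. Section 4a lists oxygenation among its key secondary hypotheses, so the result should be interpretable on one scale.

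**Working it through.** **The plan's own figure.** There is none for oxygenation. The only sample size is for the primary outcome: 60% against 40%, alpha 0.05, power 0.80. With a two-sided test, pooled variance and no continuity correction:

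n = [1.960 × √(2 × 0.5 × 0.5) + 0.842 × √(0.24 + 0.24)]² / 0.20² ≈ 96.9, so 97 per group.

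This matches section 11a and is untouched by the present point.

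**Gap between the scales.** The only pair of values in the documents is in section 9b: D = 340 − 300 = 40 units (ratio 340/300 = 1.13). Treating the two cut-offs as equivalent is an assumption. They also sit well above entry, where S/F is below 94/0.40 = 235. Read as a constant ratio instead, the gap at 235 would be 235 − 235 × 300/340 = 27.6. So 40 is an illustration, not a measured offset.

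**Added variance.** With a share q of patients on P/F and within-scale SD s (both assumed), pooling raw values multiplies the variance by 1 + q(1 − q)D²/s².

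| D | s | q | Variance factor | SD factor |
|---|---|---|---|---|
| 40 | 80 | 0.10 | 1 + 0.09 × 0.25 = 1.02 | 1.01 |
| 40 | 60 | 0.30 | 1 + 0.21 × 0.444 = 1.09 | 1.05 |
| 40 | 40 | 0.50 | 1 + 0.25 × 1 = 1.25 | 1.12 |

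**Shift in the mean difference.** If the share on P/F differs between arms by d, raw means differ by D × d with no treatment effect:

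- d = 0.05: 40 × 0.05 = 2 units
- d = 0.10: 40 × 0.10 = 4 units
- d = 0.20: 40 × 0.20 = 8 units

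**Within-patient change.** If both readings in a patient use the same ratio, a constant offset cancels and the 2 to 8 unit shift disappears. What remains is that the scales respond differently. With SpO2 held at 92 to 95%, S/F at FiO2 0.40 can run only from 92/0.40 = 230 to 95/0.40 = 237.5, a span of 7.5 units, so it moves mainly when FiO2 is changed. PaO2 has no such stated target. Section 11b does not specify an analysis of change on one scale.

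**The case against.** The best reply is that the documents never say raw values will be merged. Section 6b says what is measured, and S/F is openly called a surrogate for P/F. The wording could mean S/F for everyone, with P/F added where it can be had. The case report form in appendix B, which is not part of the text reviewed, might capture both. This stands as a caution, but it does not remove the point. All four statements use an either/or form, which favours substitution, and nothing elsewhere supplies the missing rule.

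The outcome is also defined before and after proning, so a change score may be intended. That would remove a constant offset, as shown above, but it is neither stated nor protected by a same-ratio requirement.

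Several stronger readings are tempting and are not supported:

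- *Lines will cluster in intensive care and in sicker patients.* This is a reasonable clinical inference from the mixed setting, but no section says who receives a line or how often.
- *The arms will differ substantially in line use.* With 97 per arm and half the patients having lines (assumed), the standard error of the difference is √(2 × 0.25/97) = 7.2 percentage points. By chance, a 10-point gap is 1.4 standard errors and a 20-point gap is 2.8. Differential placement after open-label allocation is possible, but the documents do not show it.
- *The gap at entry is larger than 40.* An assumed PaO2 of 65 to 75 mmHg at FiO2 0.40 gives P/F 162.5 to 187.5, against S/F 93/0.40 = 232.5, a gap of 45 to 70. The documents give no PaO2 value to support this.
- *Patients will show large false falls when a line goes in between readings.* The text permits it, but the two readings are about an hour apart, so it is likely to be uncommon.

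Finally, section 6b times its readings by proning, so a between-arm comparison also needs a defined control reading. That is a separate matter, and settling it would still leave two scales in one outcome.

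**Conclusion.** The point holds as a defect in the definition of a secondary outcome: one outcome, two numerically different scales, and no conversion, separate analysis or same-ratio rule. The documents establish this directly.

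Its size is illustrative. At a gap of 40 units, the variance factor of 1.02 to 1.25 rests on an assumed SD of 40 to 80 and 10 to 50% of patients on P/F. The shift of 2 to 8 units rests on an assumed 5 to 20 point imbalance in line use and arises only if raw levels are compared between arms. A reader might infer that the oxygenation result is certain to be biased, or that the trial's main conclusion is at risk. Neither follows: line use is undocumented, and the primary outcome and sample size do not depend on this definition. It is best labelled a cheap improvement.

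**What to change.** Make S/F the oxygenation outcome for every patient at every time point, whether or not an arterial line is present. Report P/F separately as supportive, only in patients with P/F at both readings. Suggested wording for section 6b: *SpO2/FiO2 in all randomised patients at each scheduled reading. PaO2/FiO2 is summarised separately in patients who have it at both readings. The two ratios are never combined within a patient or in a pooled comparison.* Amend sections 4a, 4b and 4c to match. The P/F subset should be read descriptively, because having a line at the second reading may itself depend on allocation.

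The cost is mainly wording. Entry and the treatment failure criteria already use SpO2 and FiO2, and the failure criteria apply to both arms. The sponsor should confirm that the case report form records both values in patients with lines, and that the definition agrees with the planned meta-trial reporting.

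There is a small downside. The more direct P/F value becomes supportive, and S/F will move mainly through FiO2 because SpO2 is kept in a narrow band. Stating this in the analysis section would help readers interpret the result.
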